1.3.4 Criteria for the selection of subjects

This study will investigate perceptions of pain, anxiety, and satisfaction in patients with a support person in the abortion procedure room ("intervention group"). Recruitment will take place at PPSWCF's Tampa Health Center.

Inclusion criteria:

Patients:

- Any patient who presents and consents for dilation and curettage
- Patient participants 17 and younger must have a legal guardian provide consent for participation, and the patient must provide assent
- Ability to provide written informed consent in English and comply with all study procedures Support Persons:
 - Any person 18 years and older who the patient selects to accompany as their support person
- Ability to provide written informed consent in English and comply with all study procedures Health Care Providers:
 - Any health center staff attending to the enrolled patient in both intervention and control arms of the study
 - Ability to provide written informed consent in English and comply with all study procedures

Exclusion criteria:

- Patients without a support person on-site willing to participate
- Patients or support persons that are unable to provide written informed consent in English and comply with all study procedures-

1.3.5. Criteria for discontinuation

Participation will be discontinued following an eligibility screening for any of the following reasons:

- Unable to receive an abortion at the health center as determined by the physician
- Subject no longer wishes to have an in-clinic abortion procedure
- The support person is perceived by staff as being dangerous or threatening to the safety of staff or patients
- Subject is found to meet exclusion criteria after informed consent has been signed
- The study is discontinued
- Subjects chooses to end participation

1.3.6. Subject recruitment

All patients presenting for an in-clinic abortion at the PPSWCF Tampa Health Center will be approached by research staff and asked if they are interested in participating in the study after they have completed the informed consent for the D&C procedure. They will be given an information sheet describing the study as well as inclusion and exclusion criteria, and will then inform research staff if they are interested in participating. If the patient is interested in participating in the study, their chosen support person will be given an information sheet describing the study, inclusion, and exclusion criteria, and will privately inform research staff if they are interested in serving as a support person. If both parties express interest in participating in the study, they will undergo the informed consent process together in a private setting.

1.3.7 Admission Procedure

Enrollment: See section 1.3.6 for details on recruitment. Enrollment in the study will occur in person.

1.3.8 Procedure:

Eligibility confirmation and consent:

After the potential patient-subject consents to have a D&C abortion procedure and both the patient and support person pass the eligibility screening, the patient and support person will undergo

the process of informed consent together where both subjects will have an opportunity to ask questions. In the cases of minors, a parent/guardian will also be present during this consent process. Both subjects will be reminded that participation is voluntary and that if either one decide not to participate, their decision will not affect the quality of the patient's routine care, however neither will be eligible to participate, as all subjects must enroll in pairs (support person and patient). The research assistant will confirm that participating subjects understand the study and meet the inclusion and exclusion criteria. Informed consent for study participation will be signed before any study-related procedures are performed and a copy of the consent will be offered to the subject. Participation is considered to start when the subject signs the Informed Consent Form.

Study procedures:

1.3.8.1 Patient Procedure and Questionnaires

- 1) After patients have consented for the D&C procedure and the study, they will complete a paper questionnaire. This questionnaire will contain demographic information and type of sedation chosen. Additionally, subjects will record their baseline level of expected pain prior to the start of the procedure. The subject will also complete the State Trait Anxiety Inventory (STAI) after the informed consent process and before the procedure starts.
- 2) On randomized intervention days, the patient will be accompanied in the procedure room by a support person.
- 3) The study physician will enter the room and perform the abortion procedure in the usual manner. The abortion procedure will remain the same on intervention days as on control days. Immediately after the procedure, the patient will complete the second 100mm VAS. Any deviations from this protocol will be recorded.
- 4) Once the patient is in the post-abortion recovery room, the patient will complete the STAI again, a post-procedure questionnaire, and the final pain level on the 100mm VAS will be recorded at least ten minutes after arrival to the recovery room. After all questionnaires have been completed and returned to research staff, the subject will be given their reimbursement gift card for participation.
- 5) The patient's complete questionnaires will be manually entered in the Qualtrics data management software which will only be managed by designated research staff. Study documents, including surveys, will be stored in a locked filing cabinet and will be accessed by research personnel only.

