1.1.2 Hypotheses and Objectives

Hypotheses:

Social support in the abortion procedure room will decrease perceived pain and anxiety levels and increase satisfaction for the patient.

- 1. Social support in the procedure room influenced the patient's health outcomes in the following areas:
 - 1. Decreased pain
 - 2. Decreased anxiety
 - 3. Increased patient satisfaction
- 2. The social support person will report that they were able to give effective support to the patient.
- 3. The physician and the nurse will find the support person effective in supporting the patient.

Null Hypothesis:

- 1. Social support in the abortion procedure room will not change patient levels of perceived pain, anxiety, or satisfaction.
- 2. The social support person will report they did not give adequate support.
- 3. The health care provider and the surgical assistant will not find the support person effective

in supporting the patient.

Objectives

Primary Aims:

- To assess a change in expected pain level from baseline, immediately after the procedure, and again ten minutes after arrival to the recovery room as determined by a 100mm visual analog scale (VAS) for patients with in-room social support during the procedure as compared to those who do not.
- To assess pre- and post-procedure state anxiety levels as determined by the 20-question State-Trait Anxiety Inventory (STAI) for patients with in-room social support as compared to patients without in-room social support.

Secondary Aims:

- To measure acceptability and effectiveness of having social support in the procedure room as reported by the surgical assistant and healthcare providers as determined by a post-procedure questionnaire.
- To evaluate if support was effectively given to the patient as reported by the support person as determined by a post-procedure questionnaire.

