4. RESEARCH INSTRUMENTS/QUESTIONNAIRES

4.1 SUBJECT DEMOGRAPHIC QUESTIONNAIRE – INTERVENTION ARM

Please fill in the information below, if applicable: Age: _____ Gestational age (How many weeks pregnant are you?) Number of children: _____ Number of previous abortions: Religion: Please circle your answers below: Ethnicity: Hispanic Non-Hispanic Race: American Indian or Alaska Native Asian Black or African American Native Hawaiian or other Pacific Islander White Two or more races **Marital Status**: Single Married Divorced Widowed Separated Are you using your insurance for the procedure? No Yes Are you receiving sedation for the procedure? Yes No What is your relation to the patient/support person?

${\bf 4.1~SUBJECT~DEMOGRAPHIC~QUESTIONNAIRE-CONTROL~ARM}$

Please fill in the information below, if applicable:

Age:						
Gestational	age (H	ow many we	eks pregnant are	e you?)		
Number of	childre	n:				
Number of j	previou	ıs abortions:				
Religion:						
	your a	nswers below				
	Non-	Hispanic				
Race:	Ame	rican Indian o	or Alaska Native			
	Asia	n				
	Black	k or African A	American			
	Nativ	ve Hawaiian o	or other Pacific Isl	lander		
	Whit	e				
	Two	or more race	S			
Marital Sta	tus:	Single	Married	Divorced	Widowed	Separated
Are you usi	ng youi	r insurance f	or the procedure	?	Yes	No
Are you rec	eiving s	sedation for	the procedure?	Yes	No	
What is you	ır relati	ion to the pa	tient/support per	rson?		

4.2 POST-PROCEDURE QUESTIONNAIRE FOR PATIENT - INTERVENTION ARM Please circle your answers below:

1.	I would rate my overall satisfaction with the procedure as: Very satisfied
	Somewhat satisfied
	Neutral
	Somewhat dissatisfied
	Very dissatisfied
2.	The amount of discomfort I experienced during the procedure was acceptable. Definitely yes
	Probably yes
	Neutral
	Probably not
	Definitely not
3.	I feel that the amount of support I received from my support person in the procedure room helped decrease my pain. Definitely yes
	Probably yes
	Neutral
	Probably not
	Definitely not
4.	I feel that I received all the support I needed from my support person in the procedure room. Definitely yes
	Probably yes
	Neutral
	Probably not
	Definitely not
La	st updated: 4/10/2017

5. The presence of my support person in the procedure room made me feel uncomfortable.
Definitely yes
Probably yes
Neutral
Probably not
Definitely not
6. If you were uncomfortable in the procedure room, were you uncomfortable due to any of the following: (Circle all applicable options)

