- Facility (ex. too cold, too small, uncomfortable chair, etc)
- Staff (instructions, attentiveness, respect, etc.)
- Beliefs (religious ideology, aversion to medical procedures, etc.)
- Other:
- Not applicable
Please provide any additional information:
7. During my procedure with my support person in the room, I felt concerned about the following: (Please circle all that apply) Privacy
Security
Other:
Not applicable

8. If I had to re-live this experience, I would prefer/choose to be accompanied in the procedure
room again.
Definitely yes
Probably yes
Neutral
Probably not
Definitely not
9. Do you have any additional comments or concerns about having a support person in the procedure room?
Thank You!

$\textbf{4.3 POST-PROCEDURE QUESTIONNAIRE FOR PATIENT-CONTROL\ ARM}$

Please circle your answers below:

1.	I would rate my overall satisfaction with the procedure as: Very satisfied
	Somewhat satisfied
	Neutral
	Somewhat dissatisfied
	Very dissatisfied
2. T	the amount of discomfort I experienced during the procedure was acceptable. Definitely yes
	Probably yes
	Neutral
	Probably not
	Definitely not
3. I pair	believe that having a support person in the procedure room would have helped decrease my
1	Definitely yes
	Probably yes
	Neutral
	Probably not
	Definitely not
4. If	I had to re-live this experience, I would prefer/choose to be accompanied in the procedure m.
	Definitely yes
	Probably yes
	Neutral
	Probably not
	Definitely not

5. Do you have any additional comments or concerns about having a support person in the procedure room?				
		Thank You!		

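### The protocol lists the arm-specific patient questionnaire ahead of the recovery-room pain VAS and does not require the VAS to be taken first

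*Protocol*

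**What the plan says.** Step 4 of Protocol section 1.3.8.1 puts the recovery-room tasks in one sentence: "the patient will complete the STAI again, a post-procedure questionnaire, and the final pain level on the 100mm VAS will be recorded". The STAI and the questionnaire are tied only to the patient being "in the post-abortion recovery room". The VAS alone has a minimum delay: it "will be recorded at least ten minutes after arrival to the recovery room". No sentence in the section says that one task must come before another.

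Step 3 places the previous pain rating earlier: "Immediately after the procedure, the patient will complete the second 100mm VAS".

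The questionnaire differs by arm. Item 3 of the intervention form (4.2) reads "I feel that the amount of support I received from my support person in the procedure room helped decrease my pain". Item 3 of the control form (4.3) asks whether patients "believe that having a support person in the procedure room would have helped decrease my" pain. Both items offer five responses, from definite agreement through neutral to definite disagreement.

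The recovery VAS is one of the time points in the primary pain aim (1.1.2). Section 1.3.11 names one change score for pain, from baseline to the recovery room, and compares the change in VAS between arms. Section 1.3.12 accepts that blinding is not possible.

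**The concern.** A self-reported endpoint should be recorded before the patient sees study material that differs by arm and refers to that endpoint. Here the listed order runs the other way. A short form with no delay attached, set beside a VAS that must wait at least ten minutes, will readily be used to fill the wait.

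The form then acts as a cue. Intervention patients have just considered whether their support person reduced their pain. Control patients have just considered whether a support person would have reduced theirs. If either exercise colours the pain mark that follows, the between-arm difference carries a component that comes from the paperwork. Randomisation does not remove it, because the form itself differs by arm, and no analysis can separate it afterwards.

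An order left open also allows practice to vary between patients and between procedure days, and the procedure day is the unit of randomisation. The VAS sheet (4.4) records the time of each mark, but the questionnaires in 4.2 and 4.3 have no time field, so the order actually used could not be recovered from the forms.

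**Working it through.** **1. Is the order fixed?** Compare the three tasks in step 4.

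| Task | Position in list | Timing rule |
|---|---|---|
| Repeat STAI | first | in recovery room |
| Questionnaire 4.2 or 4.3 | second | in recovery room |
| Final VAS | third | at least ten minutes after arrival |

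List position and the delay both point to questionnaire before VAS. There is no explicit sequence rule, so a site that takes the VAS first also complies.

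**2. Which measurements could be exposed?** The second VAS is taken immediately after the procedure, before any questionnaire. The repeat STAI is listed ahead of the questionnaire. That leaves the recovery VAS, which is the endpoint of the change score in 1.3.11.

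**3. How do the forms differ?**
- Items 1 and 2 (satisfaction, acceptability of discomfort) are the same in both arms.
- Item 3 is a pain-attribution statement in both arms: support given and helpful (4.2), support absent but potentially helpful (4.3).
- The intervention form alone asks whether enough support was received (item 4), whether the support person's presence caused discomfort (item 5), what caused any discomfort (item 6), and about privacy and security concerns (item 7).

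Item 3 taken alone suggests a shift in favour of support. Items 5 to 7 draw attention to negatives in the intervention arm only and could act the other way. The net direction is not determined.

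**4. How sensitive is the comparison to a small shift?** The protocol gives no figure for such an effect, so there is none to reproduce. What follows is an illustration under assumed shifts.

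Inputs:
- SD 23 mm and two-sided 0.05, from 1.3.2.
- 100 patients per arm. Section 1.3.2 gives 200 participants per arm, and 1.3.8 enrols them in patient and support-person pairs: 200 / 2 = 100.
- Assumed: no true effect, independent patients, and SD 23 mm for the change score. The protocol gives 23 mm for VAS scores. The SD of a change is 23 × √(2(1 − r)), which equals 23 only if the correlation r between the two ratings is 0.5.

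Standard error of the difference = 23 × √(2/100) = 3.25 mm. With 198 degrees of freedom, the smallest significant difference is 1.972 × 3.25 = 6.4 mm.

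Rejection probability from the noncentral t distribution, with noncentrality = shift / 3.25:

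| Assumed artefact between arms | Noncentrality | P(p < 0.05) |
|---|---|---|
| 0 mm | 0 | 5% |
| 2 mm | 0.61 | 9.4% |
| 4 mm | 1.23 | 23.2% |
| 6 mm | 1.84 | 45.1% |

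The test is two-sided, so the same probabilities apply whichever arm the shift favours. All three shifts are well below the 20 mm that 1.3.2 treats as clinically significant.

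**The case against.** The case for leaving the protocol alone has several parts.

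- **The order is not mandated.** A reader might infer that every patient answers the questionnaire before marking the VAS. Step 4 does not say so. This objection stands, and the point is therefore limited to what the list suggests and what is left unrequired.
- **The direction is not known.** A reader might infer from item 3 that the bias favours support. The negative items on the intervention form have no control counterpart, so the documents do not support a net direction. This stands.
- **The primary outcome as a whole is not affected.** The primary aims also include the immediate post-procedure VAS and the STAI, which come earlier as listed. This stands. One VAS time point is exposed, but it is the one that 1.3.11 names.
- **The two questions differ.** The VAS asks about current pain, while item 3 asks about the effect of support in the procedure room, on a balanced response scale. Carry-over is plausible, but nothing in the document demonstrates it. This limits the strength of the point without removing it.
- **The added risk is marginal.** Patients know their arm in any case, and 1.3.12 acknowledges the lack of blinding. That is fair, but 1.3.12 discusses dissatisfaction and anxiety at baseline; it does not discuss a cue supplied by the study's own form shortly before an endpoint. Unlike the lack of blinding, this cue can be avoided.

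None of these is a reason to prefer the listed order.

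**Conclusion.** The point holds as a weakness of procedure. Step 4 lists an arm-specific questionnaire before the recovery VAS, delays only the VAS, and does not require the VAS to come first. In an unblinded trial this lets the forms influence, differently by arm, a self-reported measure that ends the change score in 1.3.11.

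The size and direction of any effect are unknown. The 9%, 23% and 45% figures should not be read as the trial's false-positive rate. They rest on assumed shifts, an assumed SD for the change score and independent patients, whereas procedure days are randomised; correlation within days would change them. They show only that at 100 patients per arm a shift of a few millimetres, from any source, is enough to matter.

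This is a free improvement to data collection. It does not show that the pain comparison is invalid.

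**What to change.** In step 4 of 1.3.8.1, state the sequence: the repeat STAI is completed first, then the final VAS at the ten-minute point named in the primary aim, and research staff collect both before handing out questionnaire 4.2 or 4.3.

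The cost is one sentence in the protocol and a line in staff training. It needs no extra forms, patients or visits, and the sample size and clinical procedures are unchanged. If false-positive figures are quoted in support of the change, label them as illustrations under assumed shifts.

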1.3.8.2 Support Person Questionnaires

1) After the support person undergoes the informed consent process for the study, they will complete a paper questionnaire containing demographic information.

- 2) If the support person is in the control arm they will complete and return their paper surveys to the research staff before the patient is discharged, and will be given a gift card for their participation.
- 3) If the support person is in the intervention arm they will then accompany the patient to the procedure room and will be given the option of sitting or standing near the head of the patient. The support person will return the paper survey to the research staff once completed, and will be given a gift card for their participation.
- 4) The support person's complete questionnaires will be manually entered in the Qualtrics data management software which will only be managed by designated research staff. Study documents, including surveys, will be stored in a locked filing cabinet and will be accessed by research personnel only.

1.3.8.3 Health Care Staff Questionnaires

- 1) Before the health care staff participates in the study- they will undergo informed consent and sign a copy of the informed consent form. Health care staff who choose not to participate will be informed that they will not receive any negative consequences for not participating. A copy of the informed consent form will be provided to the health care staff.
- 2) After each procedure, the physician, and nurse, and other health center staff in the abortion procedure room caring for the patient will complete a post-procedure questionnaire.
- 3) The complete questionnaires will be manually entered in the Qualtrics data management software which will only be managed by designated research staff. Study documents, including surveys, will be stored in a locked filing cabinet and will be accessed by research personnel only.

A sample of the demographic survey, STAI, VAS, and the post-procedure questionnaires for the patient, support people, and health care staff is attached at the end of this proposal (see section 4).

1.3.9 Subject Reimbursement

All participating patients and support people will be eligible to receive a \$10 Target gift card after completion of study activities. Subjects who receive a gift card will sign a document acknowledging receipt of their reimbursement, and gift card logs will be stored in a locked research cabinet, as well as within the health center database. Gift card tracking data may be viewed by members of PPSWCF's finance department for tracking and record keeping purposes.

1.3.10. Data management

The PPSWCF Tampa Health Center research personnel, under the direction of the principal investigator, will create and maintain a database on the health center system, as well as in Qualtrics. Qualtrics is web-based software for building and managing online surveys and databases, and provides the ability for statistical data analysis. Collection of questionnaires and VAS data will be done on paper, and will then be directly entered into Qualtrics by research personnel. Access to this database and the paper surveys will be restricted to research staff and study investigators. Informed consent documents, the enrollment log, completed surveys and other study related documents will be maintained in a locked filing cabinet. Monitoring of data will be performed by the principal investigator and research manager to assure that the research personnel adheres to the protocol, that data are entered completely and accurately into the database, that regulatory requirements for conducting clinical research are followed, that facilities are adequate to conduct the trial, and that IRB approval is obtained. Record storage in Qualtrics is maintained for a maximum of one year. Only the research personnel are authorized entry into the research computers in the office. Appropriate firewall and virus scanning software are installed and updated routinely by the affiliate's IT department.

The Chesapeake IRB will be notified of any serious adverse experiences as per the Chesapeake IRB Policy and Procedures Manual Section. If any severe adverse events or complications occur, one of the investigators will notify the IRB within 24 hours and the investigators will meet with the Chair of the IRB to assess if the study can continue.

The principal investigator and the research manager will be responsible for the daily monitoring of subject safety, data collection, recruitment, and confidentiality and will therefore serve as the foundation of the data and safety monitoring plan. Enrollment, outcomes, and adverse events will be reviewed in weekly meetings. The research manager will be responsible for providing summaries of monitoring reports to the Chesapeake IRB at the time of annual review.

